4.4 WITHDRAWAL CRITERIA

Once a participant has been enrolled, the clinical trial site will make every reasonable effort to keep in touch with the participant for the duration of the study (26 weeks). However, it is expected that approximately 10% of participants will be lost to follow up. Participants will be free to withdraw from any part of the study at any time without any effect on their usual medical care.

The local PI may withdraw participants from the study (after consultation with the CI) in order to protect their safety and/or if participants are unwilling to follow the protocol. All randomised participants who withdraw or are discontinued from the study will be considered off study device/on study and will be followed up until the study end (26 weeks), unless they specifically withdraw their consent to further follow up. The reason for their change of status and the study procedures and assessments they have withdrawn from will be recorded in the CRF/eCRF and medical records if offered by the participant.

5. PROCEDURES AND ASSESSMENTS

5.1 IDENTIFICATION AND PRESCREENING

Patients presenting with DN at the participating clinical trial sites will be considered for this study. They will be pre-screened by a member of the direct care team and invited to speak to a member of the clinical trial site team. In addition to clinical trial sites, potential participants will also be identified from community settings who will act as participant identification centres (PICs). These PICs will conduct a search of the patient record database and suitable participants will be contacted either via letter, mailout or text to inform them about the study. Interested patients would contact the clinical trial site team directly for more information. Advertisements for the trial will be placed in clinical trial sites, PICs and posted online and will include clinical trial site contact information.

Interested patients will be given a patient information sheet to read and will be given at least 24 hours before attending an appointment for written informed consent. A pseudonymised pre-screening log will identify all approached patients, with a minimum dataset of age, sex and reason for exclusion (if applicable).

Imperial College Healthcare

Research Governance and Integrity Team

5.2 VISIT 1 - RECRUITMENT AND CONSENT

Patients will be recruited from participating clinical trial sites in the UK. Consent to enter the study will be sought from each participant only after a full verbal explanation has been given, and a patient information sheet is offered at least 24 hours beforehand. Written informed consent will be obtained before the subject is enrolled in the study. Consent is a continuous process which will be assessed during the study.

If there are substantial changes to the protocol that require re-consent, the same process will be followed. An associated updated patient information sheet will be provided to participants prior to written informed re-consent.

5.3 EQUALITY, DIVERSITY AND INCLUSION

It is important that medical devices are trialled in diverse samples of participants. To address any potential bias in trial recruitment, the following will be in place:

- Data relating to equality and diversity (age, gender, disability, ethnicity, sexual orientation recruitment site) will be collected from study participants at the initial visit. Data will be monitored on a monthly basis by the Trial Management Group (TMG) to ensure that our research sample is representative of the diabetic population. Factors limiting equality and diversity in recruitment will be reviewed and addressed.
- [name], our patient representative from an ethnic minority background, can help ensure that our study remains inclusive and assist with building rapport with other members of the community.
- The inclusion criteria are broad so that certain demographics are not excluded.
- The study will be advertised online to improve accessibility for all potential participants.
- Translations of patient information sheets and consent forms (and other patient-facing documents) will be provided to improve accessibility to non-English speaking potential participants.

5.4 VISIT 1 - BASELINE

All study assessments will be performed by a blinded researcher. These assessments can be carried out over several days to reduce participant burden. After a participant has consented into the study, they will be formally assessed against the inclusion/exclusion criteria, and the following eligibility assessments will be completed:

Research Governance and Integrity Team

- **Demographic information and vital signs** Age, sex, ethnicity, date of birth, lifestyle, socioeconomic status, weight, height, blood pressure and pulse will be collected.
- Clinical assessment Medical and drug history and other inclusion and exclusion criteria will be reviewed (i.e. whether the patient has other causes of peripheral neuropathy, severe vascular disease requiring invasive intervention, current foot ulceration prohibiting NMES device use, any implanted electronic, cardiac or defibrillator device prohibiting NMES device use, symptoms consistent with, or being treated for DVT, regularly used a NMES device within 1 year of randomisation). There are no prohibited concomitant medications for this trial.
- Pregnancy test A pregnancy test will be performed for participants
 of childbearing potential. Participants must either be of nonchildbearing potential OR be using adequate contraception for the
 duration of the study period and have a negative urine pregnancy test
 result. The urine from the point of care pregnancy test will be discarded
 immediately after the test is performed.
- Blood tests Blood samples will be taken to exclude any other causes of DN (as mentioned in 4.1.3 NEUROPATHY SCREENING).
 Blood tests will be collected and processed locally at sites.
- Michigan Neuropathy Screening Instrument (MNSI) The MNSI is a validated screening system for distal symmetrical polyneuropathies (23,24). It comprises of a patient questionnaire and a separate clinical examination of the feet. Participants must be positively screened for DN, as demonstrated by a questionnaire score of ≥4 (24)

Once eligibility is confirmed, the following further assessments will take place:

- Nerve conduction study (NCS) (central site only) The sural, common peroneal, tibial and superficial peroneal nerves will be bilaterally tested. All NCSs will be performed by a single, blinded researcher (a highly trained neurophysiologist) at the core lab at Imperial College Healthcare NHS Trust to reduce inter-operator variability. A separate Nerve Conduction Study (NCS) Protocol will outline how NCSs for this trial are conducted. If a NCS has been performed within 3 months of consent by the blinded researcher (a highly trained neurophysiologist) as part of standard of care, this NCS can be used instead, and it does not need to be repeated as part of the baseline visit.
- Quantitative Sensory Testing (QST) (central site only) Somatosensory nerve fibre function will be assessed using the German Research Network on Neuropathic Pain (DFNS) QST protocol (29).

Research Governance and Integrity Team

The battery of tests includes measures of cold and warm detection thresholds, paradoxical heat sensations, cold and heat pain thresholds, mechanical detection threshold, mechanical pain threshold, mechanical pain sensitivity, dynamic mechanical allodynia, temporal pain summation, vibration detection threshold and pressure pain threshold. Testing will take place on the worst affected limb.

- Berg Balance Scale (BBS) Mobility and balance will be assessed using the validated measure (25).
- Neuropathic Pain Symptom Inventory (NPSI) Neuropathic pain will be assessed using the validated measure (26).
- Total Symptom Score (TSS) Symptoms (paraesthesia, pain, numbness, cramp and sleep disruption) will be assessed on a 10-point Numerical Rating Scale (NRS) and scores will be combined to give a TSS out of 50.
- Monofilament test Protected sensation will be objectively assessed using a monofilament test. A 10g monofilament will be perpendicularly applied to five sites (1st, 3rd, and 5th metatarsal heads and plantar surface of the hallux and 3rd toe) of both feet for approximately two seconds each to cause the filament to bend. The participant will be asked if they felt the pressure applied or not at each site.
- Patient diary Clinical trial site staff will provide a patient diary to
 participants to collect daily device usage for the 12-week treatment
 phase (i.e. adherence to treatment). Timed used and intensity level
 setting will be recorded. Although device usage will be collected via the
 Revitive App, a diary will also be provided to verify the Revitive App
 data collected.
- Randomisation Once eligibility has been confirmed and additional baseline assessments completed, participants will be randomised to either the control group or intervention group by being allocated a study device code. They will also be assigned a pseudonymised study number unique to each individual enrolled on the trial using Sealed Envelope.
- Device set-up and device sensory and suprathreshold Clinical trial site staff will assist in setting up the allocated study device for the participant and familiarise the participant with their device. Device set-up will include creating an account for the Revitive App and setting up the therapy plan on the participants study smartphone, which will be provided. The IFU will be provided for participants to take home for home device use.

Participants will be familiarised with their allocated study device by being asked to place the soles of both feet onto the respective

Research Governance and Integrity Team

footpads. Baseline device sensory and motor thresholds will be established by systematically increasing the stimulation intensity in increments of one whilst the participant provides verbal sensory feedback. The minimal intensity, at which the participant is able to clearly feel electrical stimulation, will be recorded as the sensory threshold; and that producing visible muscle twitches of the medial gastrocnemius will be the motor threshold. The stimulation intensity will be adjusted to produce visible but non-painful contraction of the lower limb musculature at twice the individual motor threshold or as much as the participant can tolerate as comfortable (suprathreshold) and this will be recorded. Participants will be instructed to use the device at the suprathreshold level (twice the individual motor threshold or as much as the participant can tolerate as comfortable). If participants do not perceive any sensation or muscle contractions, they should be encouraged to use their study device at the highest stimulation intensity (level 99), provided there are no other concerns with using the device at this level. Participants will complete their first treatment at the clinical trial site and will be advised to complete two 30-minute sessions a day, a minimum of five hours a week for 12 weeks at home. Usage will be recorded in a patient diary and Revitive App. Treatment session reminders will be issued via the Revitive App.

Device credibility and expectancy questionnaire – After completing their first treatment session, participants will be asked to complete a modified treatment credibility and expectancy questionnaire. This is a simple questionnaire to assess participants' treatment expectancy and rationale credibility as these factors may contribute to observed differences in outcomes (27).

5.5 VISIT 2 – WEEK 3, WEEK 6, WEEK 9 (TELEPHONE CALL)

At Week 3, Week 6 and Week 9, participants will be telephoned to see if they are tolerating the device. They will be asked to continue with treatment until the end of the treatment phase (12 weeks) and to increase the stimulation intensity of the device if they feel comfortable to do so, unless they are experiencing problems which require reducing the stimulation intensity level or stopping treatment, which will be based on clinical judgement of the local PI. If there are any concerns with safety, this will be escalated to the PI who will make a final decision on if unblinding is necessary (see **3.3 BLINDING PROCESS**).

At these follow up visits, participants will be told to inform the clinical trial site staff of any change in their medication or health. These AE (safety reporting) and concomitant medication checks are important as any changes may affect

Imperial College Healthcare

Research Governance and Integrity Team

their participation in the trial, although there are no prohibited concomitant medications for the trial.

At Week 6, the MNSI Part A questionnaire and TSS will also be completed over the telephone.

At Week 9, participants will be reminded to restart their therapy plan the following week on the Revitive App. A therapy plan will be set-up for participants at baseline by clinical trial site staff on the Revitive App, however, therapy plans in the Revitive App last for 10 weeks as standard. These will need to be restarted by participants at 10 weeks to complete the 3-month treatment phase. Re-starting therapy plans are also important to ensure participants continue to receive reminders to complete their treatment sessions.

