1. INTRODUCTION

1.1 BACKGROUND

1.1.1 DIABETES AND DIABETIC NEUROPATHY

Diabetes is a major global healthcare problem. Approximately half a billion people are estimated to have diabetes worldwide, and this is forecasted to rise to 700 million by 2045 (1). In the United Kingdom (UK), an estimated 4.6 million people have diabetes, and this is predicted to rise to 5 million people by 2025. In addition, it is estimated that 1 million cases of type 2 diabetes in the UK are currently undiagnosed (2).

Diabetes is a chronic metabolic condition characterised by hyperglycaemia, which damages blood vessels and leads to macrovascular (coronary artery disease, cerebrovascular disease and peripheral arterial disease) and microvascular (nephropathy, retinopathy and neuropathy) complications. The most prevalent complication of diabetes, diabetic neuropathy (DN), affects more than 50% of people with diabetes (3,4). Distal symmetrical polyneuropathy is the most common type of DN, with symptoms ranging from numbness to burning, prickling, aching, tightness and hypersensitivity in the distal extremities.

The insensate lower limb increases the risk of developing diabetic foot ulcers (DFUs). Up to a quarter of people with diabetes will be affected by DFUs (4,5). DFUs are particularly challenging to manage when the cause is neuropathic or neuro-ischemic, because numbness in the lower limb can cause patients to walk on infected wounds without realising it (4,6). DFUs are also associated with high mortality rates, which rise even further after major lower limb amputation (4,7,8). The associated economic burden of DFUs is also high, with the cost to the National Health Service (NHS) in the UK estimated at £1 billion per year (4,9).

Guidelines for the management of DN emphasise improved glycaemic control, lifestyle modifications, footcare and pain management, however these strategies are sub-optimal. For example, glycaemic control significantly reduces the risk of DN in people with type 1 diabetes but not in people with type 2 diabetes (4,10). Pain management focuses on pharmacotherapies such as anticonvulsants and selective serotonin reuptake inhibitors, but these medications have a variety of side effects and are often only effective in the short term (11). Furthermore, only approximately 30% of people with DN experience pain, therefore the strategies for people who experience numbness are even more limited (3,4).

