The device is programmed with the Standard Programme, constructed from 15 one-minute low frequency waveforms patterns that repeat twice in each 30-minute programme. The intensity of electrical stimulus can be varied from level 0 to 99. When first using the NMES device at the baseline visit, baseline device sensory and motor thresholds will be established for participants by systematically increasing the stimulation intensity in increments of one whilst the participant provides verbal sensory feedback. The minimal intensity, at which the participant is able to clearly feel electrical stimulation, will be recorded as the sensory threshold; and that producing visible muscle twitches of the medial gastrocnemius will be the motor threshold. The stimulation intensity will be adjusted to produce visible but non-painful contraction of the lower limb musculature at twice the individual motor threshold or as much as the participant can tolerate as comfortable (suprathreshold) and this will be recorded. Participants may not perceive any sensation or muscle contractions because of their diabetic neuropathy (a disease characterised by sensorimotor dysfunction). In this case, participants should be encouraged to use the device at the highest stimulation intensity (level 99), provided there

Imperial College Healthcare

Research Governance and Integrity Team

are no other concerns with using the device at this level. Device sensory threshold and suprathreshold will also be recorded at Week 12 and Week 26 to assess any change in participants' device sensation over time. At baseline, an IFU will be given to all participants so they can use their study device at home. At Week 3, Week 6 and Week 9 participants will be contacted to see how they are tolerating their study device. During this visit and across the treatment phase, the clinical judgement of the local Principal Investigator (PI) will determine whether a participant is experiencing problems that require reducing the stimulation intensity level or stopping treatment.

Further details on the NMES device can be found in in the **Instructions for Use (IFU)** and **Investigator's Brochure (IB)**.

[figure not shown]

Figure 2: Revitive Medic Coach and power adaptor

Imperial College Healthcare

Research Governance and Integrity Team

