5.6 VISIT 3 – WEEK 12 (END OF TREATMENT PHASE)

After 12 weeks of treatment, participants will be invited to return to hospital. This will mark the end of their treatment phase and they will return their allocated study device. Assessment and data collection will be collected as follows:

- Blood test (HbA1c only)
- Michigan Neuropathy Screening Instrument (MNSI)
- Nerve conduction study (NCS bilateral testing of sural, common peroneal, tibial and superficial peroneal nerves) (central site only)
- Quantitative Sensory Testing (QST) (central site only)
- Berg Balance Scale (BBS)
- Neuropathic Pain Symptom Inventory (NPSI)
- Total Symptom Score (TSS)
- Monofilament test
- Device sensory threshold and suprathreshold
- Device experience questionnaire A simple device use questionnaire will be taken to report ease of device use and suggest any developments
- Collection of patient diary
- AE (safety reporting) and concomitant medication check

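### Between baseline and Week 12 the scheduled AE checks are telephone self-report with no skin prompt, so painless lesions of the soles that heal before the Week 12 foot examination may be missed, and later ones misdated

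*Protocol*

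**What the plan says.** Section 5.5 sets the contacts during treatment. At Weeks 3, 6 and 9, "participants will be telephoned to see if they are tolerating the device". It adds that "participants will be told to inform the clinical trial site staff of any change in their medication or health", and it names this as the AE and concomitant medication check. On the same calls participants are asked "to increase the stimulation intensity of the device if they feel comfortable to do so". No inspection of the feet, by the participant or anyone else, is mentioned.

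The next attendance in person is Week 12: "After 12 weeks of treatment, participants will be invited to return to hospital" (section 5.6). That visit has an AE check, a monofilament test on both feet, and the MNSI, of which section 5.4 says: "It comprises of a patient questionnaire and a separate clinical examination of the feet". The visit schedule in appendix 10.1 also marks the MNSI at Week 6, but section 5.5 limits that to the Part A questionnaire by telephone. The foot examination (Part B) therefore takes place at baseline, Week 12 and Week 26.

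On noticing an injury, section 1.1.1 says that "numbness in the lower limb can cause patients to walk on infected wounds without realising it". Section 3.1.2 says of the active device: "Participants may not perceive any sensation or muscle contractions because of their diabetic neuropathy". Section 3.1.3 has the sham at zero output after the second minute of each session.

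**The concern.** The collection method relies on the participant noticing a problem, and by the protocol's own account some participants may not. The device works through electrodes against the soles (section 3.1.2), where a small redness, blister or break can be both painless and out of sight. The active device stimulates throughout a session and the sham hardly at all, so an injury caused by stimulation would be expected almost only in the active arm. Events that are never collected would then come mainly from that arm.

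Safety is one of the primary objectives (section 2.1). The move to a powered trial depends on the device being judged safe (section 1.1.5), and no data monitoring committee is convened (section 9.8). The AE tables therefore carry the safety conclusion, and a table cannot show what was not asked for.

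**Working it through.** **The plan's own figure.** Section 8.1 gives 64 participants, 32 per arm, 10% loss, and 57 with primary outcome data. 64 × (1 − 0.10) = 57.6, so 57 reproduces, rounded down. This is the only related count. The protocol gives no rate of skin injury and no rate of detection.

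**How a plantar lesion could be found.**
- Baseline: in person; the first session is at the site (section 5.4).
- Weeks 3, 6, 9: telephone self-report (section 5.5), plus any unscheduled communication (Table 1).
- Week 12: in-person AE check, foot examination and monofilament test (section 5.6).
- Week 26: the same examinations (section 5.7).

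A lesion still present at Week 12 can be seen then. The gap is a lesion that is unnoticed and also healed by Week 12, or one first seen at Week 12 with unknown onset and peak severity. The protocol does not say that a finding at the foot examination becomes an AE.

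**Illustration. All rates are assumptions.** Let p be the true risk of such a lesion in the active arm, with 0 under sham; f the share of lesions that heal before Week 12; d the chance that a healed lesion was reported by telephone. Lesions that persist are all taken as found at Week 12.

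- Overall detection: D = f × d + (1 − f)
- Recorded risk difference: D × p
- Expected recorded cases: 32 × D × p
- Chance of recording at least one: 1 − (1 − D × p)^32

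With p = 10%:

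| f | d | D | Recorded difference (points) | Expected cases | Chance of at least one |
|---|---|---|---|---|---|
| full detection | – | 1.000 | 10.00 | 3.2 | 0.97 |
| 0.5 | 0.75 | 0.875 | 8.75 | 2.8 | 0.95 |
| 0.5 | 0.50 | 0.750 | 7.50 | 2.4 | 0.92 |
| 0.5 | 0.25 | 0.625 | 6.25 | 2.0 | 0.87 |
| 1 | 0.75 | 0.750 | 7.50 | 2.4 | 0.92 |
| 1 | 0.50 | 0.500 | 5.00 | 1.6 | 0.81 |
| 1 | 0.25 | 0.250 | 2.50 | 0.8 | 0.56 |

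The rows with f = 1 are the extreme case, in which the Week 12 examination finds nothing. With p = 5% the chance of recording at least one case is 0.81 at D = 1, 0.71 at 0.75, 0.56 at 0.50 and 0.33 at 0.25.

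**Which measure is affected.** Suppose detection D is equal in both arms and the sham risk is not zero. With 10% against 2% and D = 0.5, the recorded risks are 5% and 1%. The difference falls from 8 to 4 points, while the ratio stays at 5. So the counts and the absolute difference for this event shrink, and its expected ratio does not. A table of all AEs could behave differently: if background events are well reported and painless device lesions are not, the overall ratio also moves towards 1.

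**Context.** Even with perfect detection, 0 of 32 leaves a one-sided 95% upper limit of 1 − 0.05^(1/32) = 8.9%.

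**The case against.** A reader might infer something stronger: that for 12 weeks harms are sought only by telephone, in people enrolled because they cannot feel their feet, and that the safety comparison is therefore biased towards no difference. The protocol does not support that, for these reasons.

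- **Entry.** Eligibility is an MNSI questionnaire score of 4 or more (section 4.2). Loss of feeling is not a criterion, and section 1.1.1 describes symptoms from numbness to burning and hypersensitivity. The population includes people who may not notice an injury; it is not defined by that.
- **Other routes.** Table 1 accepts AE reports in any communication between visits. Week 12 is in person, with the feet examined. An unfelt lesion can also be seen, and users are prompted to hydrate their feet (section 3.1.2).
- **The calls.** They are not limited to toleration; section 5.5 names them as an AE check.
- **The comparison.** Assessors are blinded, the method is the same in both arms, and section 8.2.3 plans descriptive tables only. Equal detection leaves the expected ratio for one event type unchanged.
- **Risk level.** Section 7.1.1 states very few clinical risks, and none expected in this population if the exclusions are followed.
- **Unseen material.** The Instructions for Use, the Investigator's Brochure and the AE form are not at hand. Any of them may already ask for a skin check.

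Most of this stands, and it sets the limits of the point. It does not close the gap. Unscheduled reports also need awareness, and healed lesions are not visible at Week 12. The method that section 5.5 fixes is self-report without a prompt. A descriptive table is affected by uncollected events just as a test would be.

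**Conclusion.** The point holds in a narrow form. Scheduled AE checks between baseline and Week 12 rest on telephone self-report, in a population that includes people who may not notice foot injury. Painless lesions of the soles that heal before Week 12 may be missed, and those first found there may be misdated. Such lesions would be almost confined to the active arm, so counts and the absolute difference in harms could be understated.

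The size cannot be derived from the documents. With an assumed true risk of 10%, the recorded difference is 6.25 to 8.75 points if half of the lesions persist to Week 12, and 2.5 to 7.5 points if none do. These figures rest on the assumed risk, the assumed telephone detection of 25% to 75%, no such lesions under sham, and full detection of persisting lesions at Week 12. They show direction and rough scale only. This is a cheap improvement to data collection. It is not a fault that invalidates the safety summary.

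**What to change.** In section 5.5, add one scripted question to the AE check at Weeks 3, 6 and 9, worded identically in both arms. The participant, or someone with them, looks at both soles during the call and reports any redness, blister, burn or break in the skin. Record the answer as yes or no on the CRF and enter any positive as an AE.

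In sections 5.6 and 5.7, state that new skin findings at the Week 12 and Week 26 foot examinations are recorded as AEs.

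If the Instructions for Use or the AE form already contains such a prompt, section 5.5 should refer to it and say where the answer is recorded.

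The cost is one question on three existing calls, one CRF field and two sentences of text, with no extra visit. The downside is slightly more minor skin AEs recorded in both arms. The change concerns ascertainment only; no device or treatment rule is altered.
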